11.1 ADDITIONAL SAMPLE SIZE CONSIDERATIONS

Based on a standard 3+3 design, the phase I portion of the study will accrue *at most* 24 subjects. An additional 80 evaluable subjects will be needed for phase II. Because some subjects are subsequently found to be ineligible after central review, or inevaluable due to receiving no treatment after enrollment, accrual beyond 80 subjects is anticipated in order to ensure that 80 eligible, evaluable subjects, are available for analysis. The anticipated number of registrations for phase II is therefore approximately 88 subjects.

11.2 INTERIM ANALYSIS

Interim analyses will be performed separately for each stratum after 30 subjects have been accrued. Evaluable subjects that have been on study for 6 months or more will be included in the interim analysis, a projected 24 subjects within each stratum. At this time, if a test of the alternative hypothesis (six-month survival rate of at least 60% in the platinum sensitive stratum or at least 45% in the platinum refractory stratum) is rejected at the .005 level, this will be evidence in favor of closing the stratum to further accrual. The power to reject the alternative hypotheses (and exact alpha) will depend on the exact number of subjects analyzed. For example, on the platinum sensitive stratum, if the true survival rate is 40% and 24 subjects are available for analysis, then the power to reject the alternative of 60% would be 19% (alpha=.0022). For the platinum refractory stratum, if 24 subjects are available, the power to reject the alternative of at least 45% survival at 6 months would be 25% given a true survival rate of 25% (alpha=.0036).

11.3 PLANNED METHODS OF ANALYSIS

Six month survival and progression free survival rates, as well as response to treatment, will be calculated based on all subjects who receive the recommended Phase II dose of the drug combination. All eligible subjects accrued to phase II who have received at least one dose of each drug in the regimen will be considered as evaluable in the phase II analysis.

Survival will be estimated using the Kaplan-Meier method, separately for each stratum. Response and progression will be determined according to RECIST criteria. Overall survival is defined as the time between registration and death due to any cause. Subjects last known to be alive are censored at date of last contact. Progression free survival is defined as the date of registration to the date of first documentation of progression, or death due to any cause. Subjects last known to be alive and progression free are censored at the date of last contact. Due to the limited sample size in a Phase II setting, correlative studies will be considered exploratory in nature and will be used to formulate hypotheses that can be tested using correlative data from a Phase III setting.

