Inactivation of proteasome function allows for increased apoptosis and potentially enhanced antitumor effects in response to treatment with many chemotherapeutic agents. Combination treatment of Carfilzomib with a Topoisomerase-I (Topo-I) inhibitor (e.g., a camptothecin analogue) is anticipated to be at least additive and potentially synergistic as the apoptosis induced by camptothecins in cancer cells may not involve NF- κ B. In addition, proteasome inhibition may interfere with Topo-I degradation, a necessary step in DNA damage repair after exposure to Topo-I poisons. Thus, we hypothesize that Carfilzomib will enhance the anti-tumor efficacy of Irinotecan in relapsed small cell lung cancer.

Rationale for MTD

The phase Ib component of the current trial has completed enrollment. A total of 22 patients were screened with 16 being enrolled. No DLTs were observed at the 20/27 mg/m2 dose level. Two patients experienced DLTs at the 20/45 mg/m2 dose. One event was grade 4 thrombocytopenia lasting \geq 7days and the other was \geq grade 3 diarrhea. Cohort 2 (20/36 mg/m2) included 6 patients, with one patient experiencing a DLT. The MTD was established at the dose level investigated in Cohort 2. The recommended phase II dose has been determined to be: Carfilzomib 20/36 mg/m2 (stepped up dosing) with Irinotecan 125 mg/m2. The phase II component will investigate this combination in patients with relapsed small cell lung cancer.

2 OBJECTIVES

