8.2 POST TREATMENT FOLLOW-UP

Phase Ib: All subjects will be followed for 30 days after last treatment and until all drug-associated (possible, probably or definite) toxicities have resolved to Grade 1 or less.

Phase II: All subjects will be followed every 3 months until death or for 2 years after initial registration, or until death, or until study closure whichever occurs first.

9 ADVERSE EVENTS

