The primary endpoint for the phase II trial is the percent of subjects alive at six months. We will consider the combination of Carfilzomib and Irinotecan to be of interest in platinum sensitive subjects if the proportion of subjects alive at six months is 60% or greater, compared to a benchmark six-month survival rate of 40%. With a total of 40 eligible subjects treated at the RP2D in the platinum sensitive stratum, we will be able to test the null hypothesis that the true survival rate at six months is at most 40% versus the alternative that the true survival rate at six months is 60% or greater with a power of 79% and a one sided significance level, alpha of .04. According to this design, if at least 22 subjects out of 40 are alive at six months, we can reject the null hypothesis of a 40% six-month survival rate. This will be considered adequate evidence of promising activity for this regimen, and it may be recommended for further testing in subsequent studies. If fewer than 22 subjects are alive at 6 months, we will consider the regimen insufficiently active in this subject population. We will consider the combination of Carfilzonib and Irinotecan to be of interest in *platinum refractory* subjects if the proportion of subjects alive at six months is 45% or greater, compared to a benchmark sixmonth survival rate of 25%. For the platinum refractory stratum, 40 evaluable subjects will enable us to test the null hypothesis that the true survival rate at six months is at most 25% versus the alternative that the true survival rate at six months is 45% or greater with a power of 86% and a one-sided significance level of .054. If at least 15 subjects out of 40 are alive at six months, this will be considered adequate evidence of promising activity, and the regimen may be recommended for further testing in subsequent studies. If fewer than 15 subjects are alive at 6 months, we will consider the regimen insufficiently active in this subject population.

Secondary endpoints for both phases include response rates, safety/tolerability and the rates of specific adverse events, progression-free survival and biomarker endpoints as described in sections 10.1 and 10.2. With 40 eligible subjects in each stratum, the 6 month survival rate,

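### Section 11.3 gives two conflicting analysis sets for six-month survival: read literally, one admits six Phase Ib subjects, and the other drops Phase II subjects who received only one drug.

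*Combined protocol and SAP*

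**What the plan says.** The primary Phase II endpoint is the percentage alive at six months, tested separately in the platinum-sensitive and platinum-refractory strata. Four places bear on who is counted.

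- **Section 11.3, first sentence.** Six-month survival, PFS and response "will be calculated based on all subjects who receive the recommended Phase II dose of the drug combination". It has no restriction to Phase II and no eligibility condition.
- **Section 11.3, second sentence.** For Phase II, the rule is: "All eligible subjects accrued to phase II who have received at least one dose of each drug in the regimen will be considered as evaluable".
- **Section 11.1.** "An additional 80 evaluable subjects will be needed for phase II", and about 88 registrations are planned because some subjects will prove ineligible or "inevaluable due to receiving no treatment after enrollment".
- **Section 11.** The sensitive-stratum design is stated "With a total of 40 eligible subjects treated at the RP2D in the platinum sensitive stratum"; the refractory-stratum design is stated for 40 evaluable subjects.

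Section 1.5 (Rationale for MTD) reports that "Cohort 2 (20/36 mg/m2) included 6 patients, with one patient experiencing a DLT", and names that same combination as the recommended Phase II dose (RP2D). On follow-up, Section 8.2 says of Phase Ib: "All subjects will be followed for 30 days after last treatment", and also until drug-related toxicity has resolved to Grade 1 or less. Phase II subjects are followed every three months for up to two years from registration.

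**The concern.** The first two sentences of Section 11.3 define different sets for the same endpoint, and neither refers to the other. An analyst who follows the first would include the six Phase Ib subjects at the RP2D. Section 4.1 allowed Phase Ib subjects to have non-small cell lung cancer or another irinotecan-sensitive tumour, with any number of prior regimens. Phase II is restricted to extensive-stage small cell lung cancer after one platinum regimen. The primary rate would then rest on a mixed population, and the six-month status of some of its members need not have been collected.

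An analyst who follows the second sentence meets a different problem. Irinotecan is infused over 90 minutes before carfilzomib (Section 6.1). A subject who has an event during or after irinotecan and never receives carfilzomib leaves the denominator. The exclusion is then decided by what happened after treatment began, and such subjects may well have a poorer outlook. In a single-arm trial with a fixed count as the decision rule, one subject can decide between 21 and 22 alive.

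**Working it through.** **1. The plan's own figures.** Inputs from Section 11: n = 40 per stratum; sensitive, at least 22 alive, null 40%, alternative 60%; refractory, at least 15 alive, null 25%, alternative 45%. The formula is the exact binomial upper tail, P(X ≥ r | n, p).

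- Sensitive: P(X ≥ 22 | 40, .40) = .0392 and P(X ≥ 22 | 40, .60) = .791. The plan states .04 and 79%.
- Refractory: P(X ≥ 15 | 40, .25) = .0544 and P(X ≥ 15 | 40, .45) = .867. The plan states .054 and 86%.

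The alphas match and the powers agree to within one percentage point. The design therefore belongs to exactly 40 subjects per stratum.

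**2. The definitions side by side.**

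| Subject | 11.3, first sentence | 11.3, second sentence | 11.1 |
|---|---|---|---|
| Phase Ib, treated at 20/36 | In | Out | Not part of the additional 80 |
| Phase II, ineligible, given both drugs | In | Out | Out |
| Phase II, eligible, irinotecan only | Unclear | Out | Not inevaluable under the reason given |
| Phase II, eligible, both drugs | In | In | In |
| Phase II, never treated | Out | Out | Out |

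The sets agree only on the last two rows.

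**3. Whether the six could be analysed.** Survival is estimated by stratum (Section 11.3), and strata are defined only for Phase II (Sections 3.1 and 4.3). A Phase Ib subject has no stratum to enter.

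**4. Phase Ib follow-up.** The last carfilzomib dose of six 28-day cycles falls on day 5 × 28 + 16 = 156. Adding 30 days gives day 186, just beyond six months (about day 183). A subject who completes six cycles is therefore covered. One who stops materially earlier, with no unresolved toxicity, has no required contact at six months. The Phase Ib calendar mentions scans every three months until progression once off study, but that is not a survival follow-up rule.

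**5. Size of the one-drug exclusion.** The documents give no frequency, so this is an assumption. Suppose a fraction e of eligible, treated subjects is excluded and all of them die before six months. If true survival among all treated is p0, survival among those kept is p0 / (1 − e). The count rule is applied to 40 retained subjects.

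| e | Sensitive rate | Sensitive alpha | Refractory rate | Refractory alpha |
|---|---|---|---|---|
| 0 | .400 | .039 | .250 | .054 |
| 1% | .404 | .044 | .253 | .059 |
| 2.5% | .410 | .052 | .256 | .066 |
| 5% | .421 | .069 | .263 | .080 |

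At 2.5% the inputs are .40 / .975 = .4103 and .25 / .975 = .2564. That is about one subject per stratum (.025 × 40 = 1).

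**The case against.** The strongest reply is that the documents point to a Phase II-only set. The second sentence of Section 11.3 says so, Section 11 makes six-month survival the Phase II endpoint, Section 11.1 calls the 80 subjects additional, no subject may enter both portions, and the analysis is by stratum. This stands as evidence of intent. A reader might infer from the first sentence that the sponsor plans to pool the six Phase Ib subjects; the documents do not support that. What remains is that the first sentence is the one that names the six-month rate, and nothing limits or withdraws it.

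A reader might also infer that pooling would sharply inflate the false-positive rate, by adding up to six subjects to a stratum and keeping the cut-offs at 22 and 15. That is not a fair measure. The cut-offs are stated out of 40, and the inflation comes from holding them fixed while n grows. At n = 46, cut-offs of 25 and 17 give P(X ≥ 25 | 46, .40) = .034 and P(X ≥ 17 | 46, .25) = .048. The calculation also needs an allocation to strata and tumour types that the documents do not give, and it treats as known a six-month status that may not have been collected.

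Nor can the six be said to have only 30 days of follow-up: the period runs from the last treatment and continues until toxicity resolves.

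Finally, Section 11.1 explains attrition more than it defines an analysis set, and requiring a dose of each drug is an explicit choice. Both points are fair, and both drugs start on Day 1, so few subjects should fall in the gap. The mismatch still has to be settled, because it concerns who is counted in the primary test.

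**Conclusion.** The conflict is real and should be corrected. Section 11.3 holds two incompatible sets for the primary endpoint, and its second sentence does not agree with Section 11.1 on subjects given one drug only. The stated alpha and power are sound for 40 Phase II subjects per stratum; the fault is that the text does not consistently specify that set.

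The Phase Ib part is a contradiction in wording and carries no numerical size here. The tumour types of the six are not given, and some may have had small cell lung cancer. The one-drug part is probably small: at an assumed 2.5% excluded, all dying before six months, alpha moves from .039 to .052 and from .054 to .066. Complete early mortality is the least favourable case for a given fraction; if some of those excluded survive six months, the shift is smaller.

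**What to change.** Replace both sentences of Section 11.3 with one definition, and use the same words in Sections 11 and 11.1 for both strata: eligible subjects registered to Phase II who received any dose of either study drug, analysed by stratum. State that Phase Ib subjects are excluded from the primary test and that any results in those treated at 20/36 mg/m2 are described separately.

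The cost is a few sentences of protocol wording. No new data are needed, and the target of 40 per stratum and the cut-offs of 22 and 15 stay as they are. The downside is that a few subjects given one drug only would count in the denominator, which may make the survival rate slightly less favourable. It also changes the present each-drug rule, so the amendment should say that this is deliberate.

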- 9. Store tubes on dry ice or transfer to -80°C for storage until shipping. Record the time the sample was placed on dry ice or into -80°C as the "time processed" on the eCRF.
- 10. Send a hard copy of the eCRF "Specimen Collection Form" with this package

Samples should be shipped on Monday, Tuesday or Wednesday only. Please send notification of shipping via email to [name] on the day of shipment.

Shipping of Specimen(s)
Samples should be shipped on dry ice to: [name]
Department of Pharmaceutical Sciences
College of Pharmacy
University of Kentucky
[name]
E-mail: [contact]
[contact] Office
[contact] Fax

11 STATISTICAL ANALYSIS

The accrual rate for the phase I component is anticipated to be approximately 2-3 subjects per month, with a completion time of 6-9 months. The accrual rate for the phase II component is anticipated to be 3-5 subjects per month and will proceed separately in two strata (platinum-sensitive vs. platinum-refractory subjects).

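### Are the final pass marks of 22 and 15 alive left undefined if a stratum does not end with exactly 40 evaluable subjects?

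*Combined protocol and SAP*

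**What the plan says.** Section 11 makes survival at six months the primary Phase II endpoint and tests each stratum separately.

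- **Platinum sensitive:** null 40%, alternative 60%, one-sided alpha .04, power 79%. The design is introduced as "With a total of 40 eligible subjects treated at the RP2D in the platinum sensitive stratum". The pass mark is 22 of 40. The failure sentence follows directly and repeats the count without its denominator: "If fewer than 22 subjects are alive at 6 months, we will consider the regimen insufficiently active in this subject population".
- **Platinum refractory:** null 25%, alternative 45%, one-sided alpha .054, power 86%. The pass rule begins "If at least 15 subjects out of 40 are alive at six months". Its failure sentence also gives the count alone.

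Section 11.1 explains why more than 80 will be registered: "Because some subjects are subsequently found to be ineligible after central review", and others may never be treated. It concludes: "The anticipated number of registrations for phase II is therefore approximately 88 subjects". Section 3.1 gives each stratum its own accrual target and lets it close independently.

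Section 11.3 defines the analysis set without a limit of 40: "All eligible subjects accrued to phase II who have received at least one dose of each drug in the regimen will be considered as evaluable".

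Section 11.2 tests for futility in each stratum at the .005 level and adds: "The power to reject the alternative hypotheses (and exact alpha) will depend on the exact number of subjects analyzed". The final analysis has no matching sentence.

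**The concern.** A pass mark stated as a count has the advertised error rates at one sample size only. The design plans to over-accrue, some subjects are ruled ineligible only after central review, and every eligible treated subject is evaluable. The final number in a stratum could therefore be a few above or below 40. The plan does not say whether the count then stays fixed, is recalculated from the stated level, or is scaled as a proportion.

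The primary go/no-go decision would be at stake. With 42 evaluable sensitive subjects the three readings need 22, 23 or 24 alive. The trial is single-arm and the study team can see survival as it accrues, so an unwritten choice could in principle be made with the result in view. The interim section acknowledges dependence on the number analysed, which makes the silence at the final analysis more noticeable.

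**Working it through.** **Inputs.** Counts, nulls, alternatives, levels and n = 40 come from Section 11. The 80 evaluable of about 88 registered come from Section 11.1. The documents do not give the split of registrations by stratum or the distribution of the evaluable n, so these are assumed where used.

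**Formula.** For pass mark r among n subjects, alpha = P(X ≥ r | n, p0) and power = P(X ≥ r | n, p1), with X binomial.

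**Step 1: the plan's own figures at n = 40.**

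- Sensitive: P(X ≥ 22 | 40, .40) = .0392 and P(X ≥ 22 | 40, .60) = .791. Stated: .04 and 79%.
- Refractory: P(X ≥ 15 | 40, .25) = .0544 and P(X ≥ 15 | 40, .45) = .867. Stated: .054 and 86%.

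Both alphas agree as printed and the powers agree to within a point. The interim futility rule (stop at 7 or fewer, or 4 or fewer, alive of 24) leaves these values unchanged to three decimals. The plan's test is thus the exact one-sided binomial.

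**Step 2: three readings at other n.** Each cell gives the cut-off, with alpha and power in brackets. The exact column uses the smallest cut-off that meets the stated level. The proportion column is .55n or .375n, rounded up.

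| Stratum | n | Count held | Exact test at stated level | Same proportion |
|---|---|---|---|---|
| Sensitive | 38 | 22 (.0195, .670) | 21 (.0409, .778) if .04 is read to its two printed decimals; 22 if read strictly | 21 |
| Sensitive | 39 | 22 (.0280, .735) | 22 | 22 |
| Sensitive | 41 | 22 (.0532, .839) | 23 (.0270, .750) | 23 |
| Sensitive | 42 | 22 (.0706, .878) | 23 (.0375, .803) | 24 (.0183, .706) |
| Sensitive | 43 | 22 (.0913, .909) | 24 (.0260, .764) | 24 |
| Refractory | 38 | 15 (.0348, .801) | 15 | 15 |
| Refractory | 39 | 15 (.0439, .837) | 15 | 15 |
| Refractory | 41 | 15 (.0666, .893) | 16 (.0333, .823) | 16 |
| Refractory | 42 | 15 (.0805, .915) | 16 (.0416, .854) | 16 |
| Refractory | 43 | 15 (.0962, .933) | 16 (.0514, .882) | 17 (.0252, .808) |

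All three readings agree at sensitive 39 and 40 and at refractory 38, 39 and 40. The exact and proportion readings also agree at sensitive 41 and 43 and at refractory 41 and 42. Every alpha above the stated level comes from the count-held column.

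**Step 3: average effect with counts held, 44 registered per stratum.** Assume each registered subject is evaluable with probability 80/88, so that n ~ Bin(44, 80/88). Then P(n = 40) = .205, P(n ≥ 41) = .424 and P(n ≤ 39) = .371. Averaging over n gives alpha .0443 and .0573, and power .776 and .859. Gains and losses in n nearly cancel.

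**Step 4: a less favourable accrual pattern.** Suppose accrual continues until 40 are confirmed evaluable, while L later registrations await review. With counts held, alpha is .052/.066 at L = 1, .067/.078 at L = 2 and .086/.092 at L = 3. The plan gives no review time, so L is an assumption. Section 11 says: "The accrual rate for the phase II component is anticipated to be 3-5 subjects per month and will proceed separately in two strata". Split evenly, 3/2 = 1.5 to 5/2 = 2.5 registrations per stratum would arrive in a month's delay.

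**The case for a change.** The strongest case for a change is that the sponsor will analyse one achieved n, not an average, and under the assumption in Step 3 that n is exactly 40 only about one time in five. The failure sentences do omit the denominator. At 42 sensitive subjects the lowest and highest pass marks disagree whenever 22 or 23 are alive, which has probability 5% at a true rate of 40%, 22% at 50% and 17% at 60%. A sentence written beforehand would remove any doubt.

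Part of this stands: no text fixes the test at 40 or states a rule for another n. But much of the disagreement comes from taking the count out of a rule that prints its denominator. Without that reading, only the exact and proportion rules remain at n = 42, and they differ only at exactly 23 alive. That has probability .0375 − .0183 = .019 at a true rate of 40% and .803 − .706 = .097 at 60%. The plan states a null and a one-sided level, which points to the exact test.

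The obvious written repairs do not clearly improve the design. Limiting the test to the first 40 evaluable subjects by registration order would preserve 22/40 and 15/40, but it would create a test set different from the all-evaluable set in Section 11.3. At 42 sensitive subjects the exact test on everyone gives alpha .0375 and power .803, against .0392 and .791 for 22/40, with nobody left out. Below 40, fixing the level at the attained .0392 instead of the printed .04 would reject 21/38 (alpha .0409, power .778) and require 22/38 (power .670). About 11 points of power would then turn on a rounding choice.

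**Conclusion.** The concern describes a real but minor silence and does not call for a change. The stated alpha and power are correct at 40 per stratum. The nulls and one-sided levels in Section 11 determine the cut-off at another n, apart from rounding of the level at a case such as 21/38. Section 11.2 shows that the authors know alpha depends on the number analysed. An analyst facing 42 subjects would be expected to recompute the exact cut-off (23 or 16) and report the attained alpha.

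The large figures (alpha .071 and .081 at 42; power .67 and .80 at 38) require the counts to be carried to a denominator that the plan does not print. Even then, with 44 registered per stratum and 80/88 evaluable, the average alpha is .044 and .057. Larger averages need an assumed backlog of pending reviews, and independent closure of each stratum limits that overshoot. A positive result only makes the regimen a candidate for further testing, so an occasional one-subject ambiguity is tolerable. The conclusion rests on the exact binomial being the intended test, which the reproduction of both stated alphas supports.
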